4.3.1.5. Model Checking Diagnostics

Model checking diagnostics for dose proportionality and dose accumulation analysis will include the following:

- The Kenward and Roger method for approximating the denominator degrees of freedom and correcting for bias in the estimated variance-covariance of the fixed effects will be used.
- An unstructured covariance structure for the R matrix will be used by specifying

'type=UN' on the REPEATED line.

- In the event that this model fails to converge, alternative correlation structures may be considered such as CSH or CS.
- Akaike's Information Criteria (AIC) will be used to assist with the selection of covariance structure.
- Distributional assumptions underlying the model used for analysis will be examined by obtaining a normal probability plot of the residuals and a plot of the residuals versus the fitted values (i.e., checking the normality assumption and constant variance assumption of the model respectively) to gain confidence that the model assumptions are reasonable.

4.3.1.6. Population PK Model

A population PK model (POP PK) may be developed with all available data from this and historical studies as appropriate and will be reported separately.

4.4. Exploratory endpoints Analyses

N/A

4.5. Safety Analyses

The safety analyses will be based on the Safety Analysis Set, unless otherwise specified. The safety analyses have been detailed in Section [4.2](#).

4.5.1. Extent of Exposure

Number of days of exposure to study drug will be calculated based on the formula:

Duration of Exposure in Days = Treatment Stop Date – (Treatment Start Date) + 1

Subjects who were randomized but did not report a treatment start date (i.e., were randomized in error) will be categorised as having zero days of exposure.

The cumulative dose will be based on the formula:

Cumulative Dose = Sum of (Number of Days x Total Daily Dose)

Duration of exposure and cumulative dose will be calculated only for Period 3(Repeat dose).

4.5.2. Adverse Events

Refer to Section [4.2.2.1](#)

4.5.2.1. Adverse Events of Special Interest

There are no AEs of Special Interest in the study.

4.5.2.2. Impact of COVID-19 Pandemic on Safety Results

If required, additional COVID-19 displays would be reported if the pandemic has a major impact on trial and interpretation of the trial data.

4.5.3. Additional Safety Assessments

Refer to Section [4.2.2.2](#) and Section [4.2.2.3](#)

4.6. Other Analyses

N/A

4.7. Interim Analyses

No interim analysis has been planned for this study.

4.8. Changes to Protocol Defined Analyses

Changes from the originally planned statistical analysis specified in the protocol are detailed in [Table 1](#).

Table 1 Changes to Protocol Defined Analysis Plan

Protocol Defined Analysis	SAP Defined Analysis	Rationale for Changes

 Spirometry measurements will be summarised for FEV1 and FVC. 	
 Spirometry measurements will be summarised for FEV1 only. 	
 The changes are detailed correctly in SoA section of the protocol, but not in the Stats section of the protocol. Hence going by the SoA.

5. SAMPLE SIZE DETERMINATION

No formal statistical techniques were used to calculate the sample size for this study.

The number of participants included is deemed an adequate number to provide an assessment of safety and tolerability and pharmacokinetics measurements.

Sufficient participants with COPD will be screened and randomized to receive GSK3923868 or placebo in a 3:1 ratio with the intention of a minimum of 8 and a maximum of 12 participants to complete the study.

In total, up to 9 participants are planned to receive each dose of active drug in each period. If the true adverse outcome rate is 5%, the chance of observing at least one adverse event at a given dose is 37%. If the true adverse outcome rate is 20%, the chance of observing at least one adverse event at a given dose level is 87%. For sample size of 6 participants on active drug in each period, if the true adverse outcome rate is 5%, the chance of observing at least one adverse event at a given dose is 27%. If the true adverse outcome rate is 20%, the chance of observing at least one adverse event at a given dose level is 74%.

This level of predictivity is deemed adequate within this phase of development.

6. SUPPORTING DOCUMENTATION

6.1. Appendix 1 Study Population Analyses

Unless otherwise specified, the study population analyses will be based on the Enrolled Analysis Set. A summary of the number of participants in each of the participant level analysis set will be provided.

6.1.1. Participant Disposition

A summary of the number and percentage of participants who completed the study as well as those who prematurely withdrew from the study will be provided. Reasons for study withdrawal will be summarized. For those who have neither completed nor withdrawn, they will be categorized as on study intervention or in follow up.

A summary of study intervention status will be provided. This display will show the number and percentage of participants who have completed the scheduled study intervention, are ongoing with study intervention, or have discontinued study intervention prematurely, as well as primary reasons for discontinuation of study intervention.

All the data will be summarized based on GSK Core Data Standards.

6.1.2. Demographic and Baseline Characteristics

The demographic characteristics including age, gender, ethnicity, height/weight at screening and race will be summarized with descriptive statistics.

Past medical conditions and current medical conditions as of screening will be summarized respectively.

All the data will be summarized based on GSK Core Data Standards.

6.1.3. Protocol Deviations

Important protocol deviations will be summarized.

Protocol deviations will be tracked by the study team throughout the conduct of the study. These protocol deviations will be reviewed to identify those considered as important as follows:

- Data will be reviewed prior to freezing the database to ensure all important deviations (where possible without knowing the study intervention details) are captured and categorised in the protocol deviations dataset.
- This dataset will be the basis for the summaries of important protocol deviations.

6.1.4. Prior and Concomitant Medications

Concomitant medications will be coded using the latest version of WHO Drug dictionaries. The summary of concomitant medications will be provided by ingredient, i.e., multi-ingredient medications will be summarized for each individual ingredient rather than a combination of ingredients. The summary will be created using ingredient base names, i.e., ingredients with the same base name but different salt will appear under one base name in the summary. Anatomical Therapeutic Chemical (ATC) classifications will not appear in the summary.

Concomitant medications include any medication that was taken at some point during the on-intervention period as defined in Section 6.8 of the protocol.

6.2. Appendix 2 Data Derivations Rule

6.2.1. Criteria for Potential Clinical Importance

- **Laboratory Values**

Haematology				
Laboratory Parameter	Units	Category	Clinical Concern Range	
			Low Flag (<x)	High Flag (>x)
Platelet Count	10 ⁹ /L		31	900
RBC Count	10 ¹² /L		4.2	5.9
Hemoglobin	g/L	Male	90	180
		Female	90	180
Hematocrit	fraction of 1			1.5*ULN
RBC Indices				
MCV	fL		0.75*LLN	1.5*ULN
MCH	pg		28	32
%Reticulocytes	%		na	2*ULN
WBC Count with differentials				
Lymphocytes	10 ⁹ /L		0.6	6
Neutrophil Count	10 ⁹ /L		1.5	12
Monocytes	10 ⁹ /L		na	2
Eosinophils	10 ⁹ /L		na	0.5
Basophils	10 ⁹ /L		na	2*ULN

CONFIDENTIAL

Clinical Chemistry				
Laboratory Parameter	Units	Category	Clinical Concern Range	
			Low Flag (<x)	High Flag (>x)
Albumin	g/L		32	50
Calcium	mmol/L		2.2	3.24
Creatinine	umol/L	Male 40-49 years	69	106
		Male 50-59 years	67.2	106
		Male 60-69 years	67.2	106
		Male 70+ years	59.2	106
		Female 40-49 years	52.2	106
		Female 50-59 years	53	106
		Female 60-69 years	53	106
		Female 70+ years	55.7	106
Glucose	mmol/L		4.0	7.8
BUN	mmol/L		2.5	15
Potassium	mmol/L		3.5	5.2
Sodium	mmol/L		136	145

CONFIDENTIAL

Liver Function			
Test Analyte	Units	Category	Clinical Concern Range
Alanine Aminotransferase (ALT) / Serum Glutamic-Pyruvic Transaminase (SGPT)	U/L	High	≥2x ULN
Aspartate Aminotransferase (AST) / Serum Glutamic-Oxaloacetic Transaminase (SGOT)	U/L	High	≥2x ULN
Alkaline phosphatase	U/L	High	≥2x ULN
T Bilirubin	μmol/L	High	≥ 1.5x ULN
Direct Bilirubin	μmol/L		0 – 6

- **ECG**

ECG Parameters	Unit	Clinical Concern range	
		Lower(<x)	Upper(>x)
Absolute			
Absolute QTc Interval	msec		> 600
Absolute PR Interval	msec	< 85	> 240
Absolute QRS Interval	msec	< 70	> 120
Change from Baseline			
Increase from Baseline QTc	msec		> 60

- **Vital Signs**

Vital Parameters (Absolute)	Unit	Clinical Concern range	
		Lower(<x)	Upper(>x)
Heart rate	bpm	35	110
Respiratory Rate	breaths/pm	8	20
Systolic blood pressure	mmHg	95	160
Diastolic Blood Pressure	mmHg	55	100
Temperature	°C	35.6	37.7

- **Spirometry**

Any participant experiencing a reduction in FEV1 at the 1-hour post-dose compared to daily pre-dose value of > 20%.

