8.2.5. Clinical Safety Laboratory Tests

- See [Appendix 2](#) for the list of clinical laboratory tests to be performed and the SoA for the timing and frequency.
- The investigator must review the laboratory report, document this review, and record any clinically significant changes occurring during the study as an AE. The laboratory reports must be filed with the source documents.
- Abnormal laboratory findings associated with the underlying disease are not considered clinically significant, unless judged by the investigator to be more severe than expected for the participant's condition.
- All laboratory tests with values considered clinically significantly abnormal during participation in the study should be repeated until the values return to normal or baseline or are no longer considered significantly abnormal by the investigator or medical monitor.
 - If clinically significant values do not return to normal/baseline within a period of time judged reasonable by the investigator, the etiology should be identified and the sponsor notified.
- All protocol-required laboratory tests, as defined in [Section 10.2](#), must be conducted in accordance with the laboratory manual and the SoA ([Section 1.3](#)).
- If laboratory values from non-protocol specified laboratory tests performed at the institution's local laboratory require a change in participant management or are considered clinically significant by the investigator (e.g., SAE or AE or dose modification), then the results must be recorded.

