10.3.1. Definition of AE

AE Definition

 An AE is any untoward medical occurrence in a clinical study participant, temporally associated with the use of a study intervention, whether or not considered related to the study intervention. 
NOTE: An AE can therefore be any unfavorable and unintended sign (including an abnormal laboratory finding), symptom, or disease (new or exacerbated) temporally associated with the use of a study intervention.

Definition of Unsolicited and Solicited AE

 An unsolicited adverse event is an adverse event that was not solicited using a participant diary and that is communicated by a participant who has signed the informed consent. Unsolicited AEs include serious and non-serious AEs. Potential unsolicited AEs may be medically attended (i.e., symptoms or illnesses requiring a hospitalization, emergency room visit, or visit to/by a healthcare provider). The participants will be instructed to contact the site as soon as possible to report medically attended event(s), as well as any events that, though not medically attended, are of participant's concern. Detailed information about reported unsolicited AEs will be collected by qualified site personnel and documented in the participant's records. Unsolicited AEs that are not medically attended nor perceived as a concern by the participant will be collected during an interview with the participant and by review of available medical records at the next visit. Solicited AEs are predefined local and systemic events for which the participant is specifically questioned, and which are noted by the participant in their diary.

Events Meeting the AE Definition

 Any abnormal laboratory test results (hematology, clinical chemistry, or urinalysis) or other safety assessments (e.g., ECG, radiological scans, vital signs measurements), including those that worsen from baseline, considered clinically significant in the medical and scientific judgment of the investigator (i.e., not related to progression of underlying disease). Exacerbation of a chronic or intermittent pre-existing condition including either an increase in frequency and/or intensity of the condition. New condition detected or diagnosed after study intervention administration even though it may have been present before the start of the study.

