4.2. Primary Endpoint(s) Analyses

All safety analyses will be performed on the Safety Analysis set, unless otherwise specified.

Primary Endpoints:

- Adverse events (AEs) and serious adverse events (SAEs).
- Clinically significant changes in laboratory values, vital signs, 12-lead ECG, and spirometry measurements up to Follow Up.

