4.2.1. Definition of endpoints

Adverse events will be coded using the latest standard Medical Dictionary for Regulatory Affairs (MedDRA dictionary).

Grade 1 AEs are defined as mild. Grade 2 or higher AEs are defined as moderate or severe. This study will report AEs as mild, moderate, or severe.

CONFIDENTIAL

A study intervention-related AE/SAE is defined as an AE/SAE for which the investigator classifies the possible relationship to study intervention as “Yes”. A worst-case scenario approach will be taken to handle missing relatedness data, i.e., the summary table will include events with the relationship to study intervention as ‘Yes’ or missing.

Spirometry assessments are performed in triplicate with the highest value reported.

Whilst all data collected will be summarized, only measurements which are clinically significant at any timepoint between randomization and follow up will be reported as part of the primary endpoint.

Clinically significant values are defined as:

- Values in the potential clinical interest (PCI) ranges for laboratory values, vital signs, ECGs and spirometry.
- Values that achieve the study stopping criteria (protocol Section 7.1.3) for spirometry

The PCI ranges will be defined in the Section [6.2.1](#).

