4.2.2.2. Laboratory Data, Vital Signs, ECGs

For haematology, clinical chemistry, urinalysis, vital signs, ECG and spirometry data the following information will be summarised:

- 1) Clinically significant values at each visit
- 2) Raw and change from baseline values at each visit

Note: The first table is the only one included as part of the primary endpoint. Urinalysis data is only collected when there is an abnormal finding and so it is expected that urinalysis tables/listings will be sparse.

Laboratory Data

For laboratory data, separate tables for haematology, clinical chemistry and urinalysis tests will be produced. Laboratory evaluations including the analyses of Clinical chemistry tests, haematology tests and urinalysis, will be based on GSK Core Data Standards. Liver biochemical parameters will be included with clinical chemistry tests.

The details of the planned displays will be given in the OPS. Incidence of clinically significant laboratory parameters will be reported.

Vital Signs

The analyses of vital signs will be based on GSK Core Data Standards, unless otherwise specified.

In vital sign assessment, pulse rate, respiratory rate, tympanic temperature, and systolic and diastolic blood pressure will be assessed. Blood pressure and pulse measurement will be taken in the semi supine position.

Incidence of clinically significant vital sign parameters will be reported. Refer the normal ranges of laboratory parameters in the Section [6.2.1](#)

Further details of the planned displays will be given in OPS.

ECG

The QTc data analysis will use the collected values based on Fridericia formula.

The analysis of 12-lead ECG along with any ECG findings will be reported according to GSK Core Data Standards.

Safety ECGs will be performed in semi-supine position after at least 5 minutes rest. The parameters collected are PR, QRS, QT and QTc intervals.

Incidence of clinically significant ECG parameters will be reported. Refer the normal ranges of laboratory parameters in the Section [6.2.1](#)

Further details of the planned displays will be given in OPS.

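### The platelet low flag of 31 ×10⁹/L has no stated rationale and keeps large platelet falls out of the laboratory component of the primary endpoint

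*SAP*

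**What the plan says.** SAP 6.2.1 lists the platelet row as "Platelet Count 10 ⁹ /L 31 900": low flag below 31, high flag above 900.

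SAP 4.2.1 gives these limits their force. It defines clinically significant laboratory results as "Values in the potential clinical interest (PCI) ranges for laboratory values, vital signs, ECGs and spirometry" and adds that "only measurements which are clinically significant at any timepoint between randomization and follow up will be reported as part of the primary endpoint". SAP 4.2.2.2 plans two summaries for each type of safety data, one of clinically significant values and one of "Raw and change from baseline values at each visit", and then states: "The first table is the only one included as part of the primary endpoint".

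Adverse events and serious adverse events are the other primary component (SAP 4.2). Protocol 8.2.5 requires the investigator to review each laboratory report and "record any clinically significant changes occurring during the study as an AE". Protocol 10.3.1 counts as adverse events "Any abnormal laboratory test results (hematology, clinical chemistry, or urinalysis) or other safety assessments" that the investigator considers clinically significant, including those that worsen from baseline. Neither section gives a numeric limit.

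Neither document gives a platelet reference range, a platelet severity scale or a reason for choosing 31.

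**The concern.** The laboratory component of the primary endpoint is a rule-based check that runs alongside investigator judgement. For platelets, that check depends on one number. If the number is very low, a count can drop a long way on treatment and the primary laboratory table will still class it as not clinically significant. No second rule catches the drop: the same section has a change criterion for QTc and a within-day fall criterion for FEV1, but none for platelets.

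This matters because safety and tolerability in a new population is the primary objective and the groups are small. With 9 or 6 participants on active drug per period (SAP 5), one unflagged case is 1/9 = 11% or 1/6 = 17% of the group at that dose. The routine follow-up contact is a telephone call with no laboratory test (protocol 1.3.1). A count still falling at the last scheduled sample would therefore not normally be seen to go lower.

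**Working it through.** The plan states no figure derived from the platelet limit, so there is none to reproduce. The check uses the limits in SAP 6.2.1 plus two labelled assumptions.

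**1. Width of each row.** Haematology rows measure different quantities, so their low limits cannot be compared directly. The ratio of high flag to low flag within a row has no units and can be compared. For the rows with two absolute limits:

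| Row | Low | High | High/low |
|---|---|---|---|
| Platelets | 31 | 900 | 900/31 = 29.0 |
| Lymphocytes | 0.6 | 6 | 10 |
| Neutrophils | 1.5 | 12 | 8 |
| Haemoglobin | 90 | 180 | 2 |
| RBC count | 4.2 | 5.9 | 1.4 |
| MCH | 28 | 32 | 1.14 |

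The platelet row is almost three times as wide as the next widest. The ratio alone does not show which end is out of line.

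**2. Fall needed to be flagged.** Fall = 1 − 31/baseline. Baseline counts are not in the documents, so a range is assumed (×10⁹/L):

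- 150: 1 − 31/150 = 79.3%
- 200: 84.5%
- 250: 87.6%
- 300: 89.7%
- 400: 92.2%

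The flag needs a value strictly below 31, so the fall must exceed these figures. From 250, falls to 100, 75 or 50 (60%, 70% or 80%) are not flagged.

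**3. Low end against a laboratory limit.** The one haematology low flag tied to the laboratory's own limit is MCV, at 0.75 × LLN. Assuming a platelet LLN of 130 to 150 (not in the documents), 31 is 31/130 = 0.24 to 31/150 = 0.21 of LLN. A multiple of 0.75 would give 0.75 × 130 = 97.5 to 0.75 × 150 = 112.5.

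**4. Effect side by side.** Under SAP 6.2.1, a platelet fall from an assumed 250 to 50 does not enter the primary laboratory table. A sodium of 135 mmol/L (low flag below 136) and an MCH of 27.9 pg (low flag below 28) both do.

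**The case against.** The strongest reply is that little is hidden. A reader might infer that a large platelet fall would escape the primary safety endpoint altogether. The documents do not support that. Adverse events are a primary component, and the protocol tells the investigator to record clinically significant laboratory changes as adverse events. All platelet values also appear in the raw and change summaries, where a large fall among about 12 participants should be visible. No hypothesis is tested, and the study halting criteria in protocol 6.5.1.2 do not use these flags. All of this stands, and it confines the point to the laboratory component.

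A reader might also infer that the row can never fire. It can: any count below 31 is flagged.

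Nor do the documents prove that 31 is a mistake. The row is wide at both ends, which could reflect an intended extreme-value flag. The table follows no single scale: haematocrit has no low flag, and several white-cell rows have none. Platelet count and MCV are different quantities, so the MCV multiple shows a form of rule, not the right value. The risk table in protocol 2.3.1 names no haematological risk. The SAP version history says 6.2.1 was revised because its ranges and units did not match the laboratory's values. That makes a check reasonable but does not show an error here.

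The calcium row (2.2 and 3.24 mmol/L) might look like a parallel defect. Nothing in the documents requires symmetric flags, and the asymmetry appears only against an assumed upper limit, so no point is made of it.

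What the objection leaves untouched is that the rule-based check for platelets is very insensitive and unexplained. Investigator judgement is the only other route into the primary endpoint.

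**Conclusion.** The concern holds for the laboratory component of the primary endpoint, not for the endpoint as a whole. That the limit controls this component follows from SAP 4.2.1, 4.2.2.2 and 6.2.1 alone, as does the 29-fold width against 10-fold or less in the other rows.

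The size of an unflagged fall, up to 79% to 92%, rests on assumed baselines of 150 to 400. The comparison with a normal limit rests on an assumed LLN of 130 to 150. These falls are called large rather than severe because the documents do not grade platelet counts.

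The limit should be changed because the affected table is primary, no rationale for 31 is given, and the correction is cheap.

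**What to change.** Before unblinding, replace the fixed platelet low flag in SAP 6.2.1 with a limit tied to the local laboratory's LLN, in the form the table already uses for MCV. As an example only, 0.75 × LLN would give about 98 to 113 ×10⁹/L under the assumed LLN. The sponsor's safety physician should confirm the multiple, and the SAP should record the reason for it.

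If the data are already unblinded, keep the planned table and add the new limit as a labelled supplementary display.

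The cost is one table cell, a re-run of the flagging program and possibly a few more flagged values to explain. The change affects an analysis flag only and alters no stopping rule or participant management.

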1.3. Schedule of Activities (SoA)

1.3.1. Screen and Follow Up

Procedure	Screening ¹ (up to -30 days before Day 1)	Early Discontinuation/Withdrawal Visit (7 ± 2 days post last dose)	Follow Up Phone Call (7 to 14 days post last dose)
Phone Call			X
Informed Consent	X		
Review Inclusion and Exclusion Criteria	X		
Demography	X		
Medical & Disease History	X		
Full Physical Examination (includes height, weight and BMI)	X		
Brief Physical Examination		X	
Alcohol Urine Test	X	X	
Urine Drug Screen	X	X	
COVID-19 Screening ²	X	X	
AE Review		X	X
SAE Review	X	X	X
Concomitant Medication Review	X	X	X
Inhaler Training	X		
Spirometry (FEV1 & FVC) ³	X	X	
Vital Signs ⁴	X	X	
12-Lead Safety ECG ⁵	X	X	
Safety Laboratory Assessment ⁶	X	X	
Urinalysis	X	X	
Serum FSH and Estradiol ⁷	X		
Urine Pregnancy Test	X	X	
HIV, Hepatitis B and C Screening	X		

Procedure	Screening ¹ (up to -30 days before Day 1)	Early Discontinuation/Withdrawal Visit (7 ± 2 days post last dose)	Follow Up Phone Call (7 to 14 days post last dose)
PK Blood Sample		X	

1. Screening may be performed across multiple visits if necessary.
2. To be performed according to local site policy.
3. Pre- and post-bronchodilator FEV1, predicted FEV1 and FVC are needed at screen only.
4. Includes systolic and diastolic blood pressure, heart rate, respiration rate and tympanic temperature
5. Triplicate ECGs will be obtained at screening and single ECGs at all other occasions.
6. Clinical chemistry, hematology.
7. As needed in women of nonchildbearing potential only

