
11. Current enrolment or past participation in a clinical trial and has received an investigational product within the following period before the first dosing day in this study: 30 days, 5 half-lives or twice the duration of the biological effect of the investigational product (whichever is longer).

DIAGNOSTIC ASSESSMENTS

12. Positive human immunodeficiency virus (HIV) antibody test.
 
13. Positive pre-study drug (except for as results of opioids prescribed for medical reasons and/or inadvertent consumption of poppy seeds, see Section 6.8) /alcohol screening result.
 
14. Presence of HBsAg/anti-hepatitis B core antibodies (IgM) at screening or within 3 months prior to first dose of study intervention.
 
15. Positive hepatitis C antibody test result at screening or within 3 months prior to first dose of study intervention.
 
16. QTcF > 450 msec at screening visit based on the average of triplicate ECGs.
 
17. A positive laboratory confirmation of COVID-19 infection, or high clinical index of suspicion for COVID-19

OTHER EXCLUSIONS

18. History of regular alcohol consumption within 6 months prior to the study defined in Germany as:
 
 • An average daily intake of pure alcohol of > 24 g per day for males and >12 g per day for females. 
19. Sensitivity to the study intervention or components thereof (including CCI [REDACTED], [REDACTED], or drug or other allergy that, in the opinion of the Investigator or medical monitor, or vulnerable participants (e.g., participants in detention, protected adults under guardianship, trusteeship, or committed to an institution by government or juridical order) contraindicate participation in the study.

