7.1.2. QTc Stopping Criteria

The Fridericia QT correction (QTcF) formula will be used in the study.

A participant that meets either bulleted criteria based on the average of triplicate ECG readings will be considered for withdrawal from the study intervention:

- $QTcF > 500$ msec
- Change from baseline: $QTcF > 60$ msec

Baseline QTcF will be based on the pre-dose ECGs collected before the first dose.

If a clinically significant finding is identified after enrolment, the investigator or qualified designee will determine if the participant can continue in the study and if any change in participant management is needed. This review of the ECG printed at the time of collection must be documented. Any new clinically relevant finding should be reported as an AE.

Note: Single safety ECG assessments are performed following enrolment in this study. If a single ECG should meet the criteria above, obtain two further ECGs over a brief period (e.g., 5 to 10 minutes). The averaged QTcF value of the 3 ECGs should be used to determine whether the participant should be withdrawn from the study.

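### The SAP's absolute QTc flag (above 600 msec) can leave an ECG that meets the protocol's QTcF stopping criterion (above 500 msec) out of the primary-endpoint ECG table when baseline is above 440 msec or missing

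*SAP*

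**What the plan says.** SAP 4.2.1 restricts this part of the primary endpoint to clinically significant measurements and defines these in two bullets. The first, which covers ECGs, takes any value in the ranges of SAP 6.2.1. The second adds "Values that achieve the study stopping criteria (protocol Section 7.1.3) for spirometry". No such addition is made for QTc. SAP 4.2.2.2 then states that, of the ECG summaries, only the table of clinically significant values belongs to the primary endpoint.

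SAP 6.2.1 gives two QTc rows: "Absolute QTc Interval msec > 600", and an increase from baseline above 60 msec. Protocol 7.1.2 lists two stopping criteria: QTcF above 500 msec, and a change from baseline above 60 msec. A participant who meets either one is considered for withdrawal from treatment.

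The quantity is the same in both documents, since SAP 4.2.2.2 states: "The QTc data analysis will use the collected values based on Fridericia formula".

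**The concern.** A reader would expect an ECG serious enough to raise withdrawal to count as clinically significant in the table that reports the primary endpoint. As written, it may not.

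The gap looks unintended. For FEV1 the SAP flag is the same as the stopping criterion in protocol 7.1.3, and SAP 4.2.1 names that criterion a second time. For ALT the SAP flag (at least 2 times ULN) lies below the stopping value in protocol Appendix 6 (at least 3 times ULN). Among these three measures, which have both a flag and a stopping value that can be compared, only absolute QTc is flagged above its stopping value.

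The table deals in small numbers. Protocol 9.2 plans up to 9 participants on active drug in each period, so one uncounted participant is 1/9, or about 11%, of a dose group. Under protocol 6.5.1.2, two participants meeting the QTc criteria halt dosing temporarily. The study could thus pause for QTc while its primary-endpoint table shows no clinically significant QTc value.

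**Working it through.** The 600 msec limit is a chosen threshold with no derivation in the plan, so there is no figure to reproduce. The check compares the two rules.

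**Inputs**
- SAP flags (6.2.1): QTc > 600, or QTc − B > 60, where B is baseline.
- Absolute stopping criterion (protocol 7.1.2): QTcF > 500, on the mean of three ECGs. SAP 6.2.5 also averages triplicates, so the comparison is like for like.
- Baseline: the pre-dose ECG before first dose (protocol 7.1.2 and 8.2.3; SAP 4.1.2). A missing baseline stays missing (SAP 4.1.2), and the rise flag cannot then be applied.
- Entry limit (protocol 5.2): "QTcF > 450 msec at screening visit based on the average of triplicate ECGs" is an exclusion, so 441 to 450 msec at screening is eligible.
- Type of reading (protocol 1.3.1, footnote 5): "Triplicate ECGs will be obtained at screening and single ECGs at all other occasions". Baseline is therefore a later reading, scheduled as a single ECG, and the 450 msec limit does not cap it.

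**Rule for an uncounted value**

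The value meets the absolute stopping criterion but neither QTc flag:

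QTcF > 500, and QTcF ≤ 600, and QTcF − B ≤ 60,

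which is 500 < QTcF ≤ min(600, B + 60).

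This range contains values only if B + 60 > 500, that is, B > 440. If B is missing it is 500 < QTcF ≤ 600.

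| Baseline B (msec) | B + 60 | Uncounted QTcF, whole msec | Rise from baseline |
|---|---|---|---|
| 440 or below | 500 or below | none | – |
| 441 | 501 | 501 | 60 |
| 445 | 505 | 501–505 | 56–60 |
| 450 | 510 | 501–510 | 51–60 |
| 460 (assumed) | 520 | 501–520 | 41–60 |
| 470 (assumed) | 530 | 501–530 | 31–60 |
| missing | – | 501–600 | not computable |

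The rows for 460 and 470 are assumptions, because the documents give no data on how far the pre-dose reading may drift from screening. A search in steps of 0.1 msec found the first affected baseline at 440.1 msec, which confirms the cut-off.

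**What the 600 msec row contributes.** A value above 600 is already a rise above 60 whenever B ≤ 540, since 600 − 540 = 60. The row is the only QTc trigger when B is above 540 msec or missing.

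**After the change.** If the protocol 7.1.2 criteria count as clinically significant, the uncounted range is empty at every baseline tested and when baseline is missing.

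**The case against.** The strongest reply is that very little is lost. The case needs a participant, among about 12, with a baseline above 440 msec, a QTcF above 500 msec and a rise of no more than 60 msec. Within the screening limit the gap is at most 10 msec wide. A missing baseline is unlikely, because a pre-dose ECG is scheduled and the screening ECG might serve as the last value before dosing, although the Day 1 wording in SAP 4.1.2 leaves that unclear. All of this stands and limits the size of the point.

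The value also remains visible. SAP 4.2.2.2 summarises "Raw and change from baseline values at each visit", and SAP 4.1.1 includes the maximum among the summary statistics. Protocol 7.1.2 adds: "Any new clinically relevant finding should be reported as an AE". Adverse events are themselves a primary endpoint, and reasons for withdrawal are summarised (SAP 6.1.1). This stands too. But the raw and change summaries are outside the primary endpoint by the SAP's own statement, and the adverse event route depends on a judgement of relevance. Neither puts the value in the ECG table.

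Third, protocol 9.4.2.2 leaves these ranges to the SAP, so choosing 600 breaks no protocol rule and needs no entry among the changes in SAP 4.8. That is correct. Leave to set the range does not, however, explain a range under which an ECG at the stopping level is not clinically significant.

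Finally, the temporary halt works from the protocol's criteria during conduct, not from the SAP table. Participant safety is not affected, and the point concerns reporting only. The comparison with ALT and FEV1 covers few items: the liver algorithm in protocol Figure 2 is not reproduced in the text reviewed, and most laboratory flags have no stopping value to compare with. It suggests an oversight but does not prove one.

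**Conclusion.** The point holds. As written, the primary-endpoint ECG table omits as a QTc finding any value with 500 < QTcF ≤ min(600, baseline + 60). That range is empty at baselines of 440 msec or below. It reaches 510 msec at a baseline of 450 and 600 msec when baseline is missing. An ECG in the range could still enter the table through a PR or QRS flag, but not for its QTc.

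The result rests on the thresholds as printed, on Fridericia values throughout, and on the SAP's statement of which table belongs to the primary endpoint. Only the rows for 460 and 470 msec use assumed baselines. The documents do not allow an estimate of how often such a reading would occur. The expected impact is small, but the inconsistency lies in a primary-endpoint definition and should be fixed. No view is taken on which QTc threshold is clinically right.

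**What to change.** Reconcile SAP 4.2.1 and 6.2.1 with protocol 7.1.2 for reporting. Either of two edits closes the gap:

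- extend the second bullet of SAP 4.2.1 so that values meeting the stopping criteria of protocol 7.1.2, as well as 7.1.3, count as clinically significant; or
- align the absolute QTc reporting flag in SAP 6.2.1 with the protocol's own criterion.

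If 600 msec is intended, state the reason in the SAP and note that some ECGs meeting the stopping criterion will not appear in the table.

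The cost is one phrase or one table cell. No new data are needed, and the stopping rule and study conduct do not change.
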